8.6.1.1 Partial dates for adverse events

Onset date of AEs

If only the day of the AE onset date is missing, the missing day will be set to:

First day of the month that the event occurred, if the onset YYYY-MM is after the YYYY-MM of first study treatment

The day of the first study treatment, if the onset YYYY-MM is the same as YYYY-MM of the first study treatment

The date of informed consent, if the onset YYYY-MM is before the YYYYMM of the first treatment

If both of the day and month of the onset date of an AE are missing, the onset date will be set to:

January 1 of the year of onset, if the onset year is after the year of the first study treatment.

The date of the first treatment, if the onset year is the same as the year of the first study treatment

The date of informed consent, if the onset year is before the year of the first treatment

Resolution date of AEs

If only the day of the AE resolution date is missing, the missing day will be set to:

The last day of the month of the occurrence. If the patient died in the same month, then set the imputed date as the death date

If both day and month of the resolution date of an AE are missing, the date will be set to:

December 31 of the year of occurrence. If the patient died in the same year, then set the imputed date as the death date

8.6.1.2 Partial dates for prior/concomitant medication

Start date of prior/concomitant medication

If only the day is missing, then the start date of a therapy will be set to the first day of the month that the event occurred.

If both the day and month are missing, then the start date of a therapy will be set to January 1 of the year of onset.

If the start date of a therapy is completely missing, then the date will be set as following.

- If the end date is not a complete date, then the start date will be set to the date of the first study visit.
- If the end date is a complete date,
 - And the end date is after the date of the first study visit then the start date will be set to the date of the first study visit.
 - Otherwise, the start date will be set to the end date of the therapy.

End date of prior/concomitant medication

If only the day is missing, then the end date of a therapy will be set to the last day of the month of the occurrence.

If both the day and month are missing, then the end date of a therapy will be set to December 31 of the year of occurrence.

If the end date of a therapy is completely missing, then the date will be set as following

- If the start date is not a complete date, then the end date will be set to the date of the last study visit.
- If the start date is a complete date
 - And the start date is prior to the date of the last study visit then the end date will be set to the date of the last study visit.
 - Otherwise, the end date will be set to the start date of the therapy.

8.7 Analysis plan for ADA data

Serum samples for ADA assessments will be conducted utilizing a tiered approach (screen, confirm, titre) and ADA data will be collected at scheduled visits shown in SOA Table 2 and Table 3 in the CSP. ADA result from each sample will be reported as either positive or negative. If the sample is positive, the ADA titre will be reported as well. In addition, the presence of neutralizing antibodies (nAb) will be tested in ADA-positive samples using a ligand binding assay.

In general, patients with a missing baseline ADA assessment will be assumed to be ADA negative at baseline as a conservative approach to ensure that all patients are included in all analyses. If a positive ADA titre result is reported as <15, then the titre will be imputed as 15

for titre summaries. ADA results from samples collected post-dose instead of pre-dose on an IP administration day are considered unreliable and should be excluded from all derivations.

For all patients, the following variables will be derived based on the data collected during the DB period. Results will be listed separately.

- Patients who are ADA positive at any time during the study, including baseline and/or post-baseline (also generally referred to as ADA positive). The proportion of ADA-positive patients in a population is known as ADA prevalence.
- Patients who are ADA negative at all assessments, including baseline and post-baseline (also generally referred to as ADA negative).
- Patients who are ADA positive at baseline only.
- Patients who are ADA positive at baseline and at least one post-baseline assessment.
- Treatment-emergent ADA positive (referred to as ADA incidence). A positive post-baseline result and either of the following statements holds:
 - Baseline is ADA negative and at least one post-baseline assessment is ADA positive. This is called treatment-induced ADA positive.
 - Baseline is ADA positive, and the baseline titre is boosted by greater than the variability of the assay (i.e. ≥ 4 -fold increase) at ≥ 1 post-baseline timepoint. This is called treatment-boosted ADA positive.
- Non-treatment-emergent ADA positive: Patients who have a baseline and at least one post-baseline ADA assessment, and who are ADA positive but not fulfilling the conditions above for treatment-emergent ADA positive.
- Patients who are persistently ADA positive, which is defined as ADA negative at baseline and having at least 2 post-baseline ADA positive measurements with ≥ 16 weeks between first and last positive, or an ADA positive result at the last available post baseline assessment.
- Patients who are transiently ADA positive, defined as ADA negative at baseline and at least one post-baseline ADA positive measurement and not fulfilling the conditions for persistently positive.
- Patients who are treatment-emergent ADA positive with maximum post-baseline titre $>$ median of maximum post-baseline titres. The median of maximum post-baseline titres will be calculated based on the maximum post-baseline titre of each ADA positive patient within each treatment group.
- nAb prevalence; defined as nAb positive at any visit including baseline and/or post-baseline (also referred to as nAb positive).
- nAb incidence; defined as nAb negative at baseline (or ADA negative at baseline) and nAb positive at any post-baseline visit. Patients who are ADA-negative at baseline are included to ensure that all patients who are nAb positive for the first-time post-baseline

satisfy this definition, given that all patients who are ADA negative at baseline do not have a nAb result reported.

Similar ADA responses described for the DB period will be derived for the OLE; specific considerations for the OLE period are provided as follows. Baseline value for the OLE period is based on the last available value collected prior to the 1st dose in OLE, not from the beginning of the DB period.

- Newly persistently positive: Patients who are ADA negative at baseline and positive at ≥ 2 post-baseline assessments (with ≥ 16 weeks between first and last positive) or positive at last post-baseline assessment.
- Stable persistently positive: Patients who are ADA positive at baseline and ≥ 2 post-baseline assessments (with ≥ 16 weeks between first and last positive).
- Newly treatment-emergent ADA-positive (ADA incidence): Patients who are either newly treatment-induced positive or treatment-boosted ADA positive.
 - Newly treatment induced ADA positive: Patients who are not ADA positive at any time in DB period but are ADA positive post-baseline for the first time in the OLE period.
 - Treatment-boosted ADA-positive: At least 1 of patient's post-baseline titres in the OLE period is ≥ 4 -fold increase of the baseline titre.
- Non-treatment-emergent ADA positive: Subjects who have a baseline and at least one post-baseline ADA assessment in the OLE period, and who are ADA positive but not fulfilling the conditions above for newly treatment-emergent ADA positive.
- Transiently positive: Patients having at least 1 post-baseline ADA-positive assessment and not fulfilling the conditions of either newly persistently positive or stable persistently positive.

Similarly, ADA responses described for the DB period will be derived for the on-study period; specific considerations for the on-study period are provided as follows. Baseline value for the on-study period is based on the last available value collected prior to the 1st dose in DB period.

- Patients who are persistently ADA positive
 - 6-month persistently ADA positive: Subjects who are ADA negative at baseline and having ≥ 2 post-baseline ADA positive assessments (with ≥ 6 months between first and last positive) or positive at the last available post baseline assessment.
 - 12-month persistently ADA positive: Subjects who are ADA negative at baseline and having ≥ 2 post-baseline ADA positive assessments (with ≥ 12 months between first and last positive) or positive at the last available post baseline assessment.

The responses above will be summarised as counts and percentages by treatment group over the DB period, OLE period, and the on-study period as appropriate. The maximum ADA titre will also be summarised for patients in each of the ADA positive response categories listed above. The maximum titre will be derived based on all available ADA titres reported for each patient, including any unscheduled assessments.

ADA response (positive or negative) and titre will be summarised at baseline and at all scheduled post-baseline visits by treatment group using derived visit windows (refer to Section 3.1.2 for detailed definition of visit windows) in each study period. In the event a patient has more than one result within a given visit window, the maximum ADA titre will be used in the by-visit summary. In addition, the ADA response will be presented cumulatively. The cumulative ADA response is positive for a specific visit if a positive ADA result is detected at any time point up to and including the specific visit. If all ADA result are negative up to the specific visit, then the cumulative ADA response is negative for that visit. A summary of the number and percentage of patients who are ADA positive at a post-baseline assessment for the first time by visit will also be presented. A line plot of serum concentrations over time will be provided by ADA categories.

The proportion of patients with positive nAb response will be summarised by visit. Key patient information will be listed for patients with positive ADA results, including ADA status, nAb status, titer, benralizumab serum concentration, and blood eosinophil level.

All analyses will be conducted by treatment group on the safety analysis set for the DB period and the on-study period, and on the OLE analysis set for the OLE period, unless otherwise specified. All ADA results will be listed. Results from the DB period will be reported at the primary DBL while remaining results from OLE period and the on-study period will be reported at the final DBL.

ADA and blood eosinophil levels

Eosinophil levels will be summarised by visit and for the following ADA response categories of patients:

For the DB period: ADA negative, ADA positive, treatment-emergent ADA positive, non-treatment-emergent ADA positive, ADA persistently positive, ADA transiently positive, nAb-positive, and treatment-emergent ADA positive with maximum post-baseline titer > median of maximum post-baseline titre.

For the OLE period: ADA negative, ADA positive, newly treatment-emergent ADA positive, non-treatment-emergent ADA positive, newly ADA persistently positive, stable ADA persistently positive, nAb-positive, ADA transiently positive, and treatment-emergent ADA positive with maximum post-baseline titer > median of maximum post-baseline titre.

For the on-study period: ADA negative, ADA positive, treatment-emergent ADA positive, non-treatment-emergent ADA positive, ADA persistently positive, ADA 6-month persistently positive, ADA 12-month persistently positive, ADA transiently positive, treatment-emergent

ADA positive with maximum post-baseline titer > median of maximum post-baseline titre and nAb-positive.

A line plot of blood eosinophil levels by visit and ADA status will also be presented.

ADA and efficacy

The effects of ADA on the co-primary endpoints calculated during the DB period will be evaluated through summary statistics by treatment group and ADA status (i.e. ADA negative, ADA positive, treatment-emergent ADA positive, non-treatment-emergent ADA positive, ADA persistently positive, ADA transiently positive, nAb-positive, and treatment-emergent ADA positive with maximum post-baseline titer > median of maximum post-baseline titre). Due to the expected small number of ADA positive patients in the placebo group, no formal statistical comparisons of benralizumab versus placebo by ADA status (positive/negative) are planned.

ADA and safety

Adverse events during the DB period and the OLE period will be summarised by treatment group and ADA status (i.e. ADA negative, (newly) TE-ADA positive, and non-TE-ADA positive) over safety analysis set and OLE analysis set, respectively. The potential impact of ADA on hypersensitivity will also be assessed.

ADA and PK

Similarly as blood eosinophil levels, benralizumab serum concentrations will be summarised by treatment group, visit and ADA status for patients in the PK analysis set for the DB period, OLE period, as well as on-study period.

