3. PRIMARY AND SECONDARY VARIABLES

3.1 General principles

3.1.1 Study periods for data summary

The following study periods will be derived for reporting purposes:

- Double-blind period: this is defined as the period starting on the date of randomization (for efficacy) or date of first dose of study treatment (for safety), and ending on the date of first OLE dose (for those who entered the OLE right after DB completion), or the date of the Week 56 Visit (for those who did not enter the OLE after DB, or those who entered the DB follow-up period per CSP v1.0 and v2.0). For patients who discontinued the study before the Week 56 Visit, the DB period ends on the last participation date.
 - Specifically, patients who enter the OLE period will receive their first OLE dose at the Week 56 Visit, after completion of all visit-related assessments. Therefore, all assessments at the Week 56 Visit are counted under the DB

period, and the first OLE dose (i.e. last procedure at the visit) indicates the start of the OLE period.

- Extended follow-up period, off treatment (applicable to CSP v1.0 or v2.0):
 - for patients who did not enter the OLE: this is defined as the period starting on the date after the end of DB period and ending on the date of last participation in the study.
 - for patients who were followed up off-treatment after DB period and then entered the OLE: this is defined as the period starting on the date after the end of DB period and ending on the date of first OLE dose.
- Open-label period: this is defined as the period starting on the date of first OLE dose and ending on the date of last participation in the study.
- On-study period: this is defined as the period starting on the date of randomization (for efficacy) or date of first dose of study treatment (for safety) and ending on the date of last participation in the study.

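### SAP 8.7 classes an OLE patient with a DB-positive sample, a negative OLE baseline and a positive OLE sample as non-treatment-emergent, whatever the OLE titre

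*SAP*

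**What the plan says.** All the definitions are in SAP 8.7.

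- **DB rule.** Treatment-induced means "Baseline is ADA negative and at least one post-baseline assessment is ADA positive". Nothing before baseline matters.
- **OLE baseline.** "Baseline value for the OLE period is based on the last available value collected prior to the 1st dose in OLE". For patients who enter the OLE straight after DB this is normally the Week 56 sample. SAP 3.1.1 assigns that sample to DB: "all assessments at the Week 56 Visit are counted under the DB" period.
- **OLE, newly treatment-emergent** (also labelled ADA incidence). Either of two conditions suffices: "Newly treatment induced ADA positive: Patients who are not ADA positive at any time in DB period but are ADA positive post-baseline" (the first positive must fall in the OLE), or boosted, where at least one of the "post-baseline titres in the OLE period is ≥ 4 -fold increase of the baseline titre".
- **OLE, non-treatment-emergent.** Patients with a baseline and at least one later OLE assessment "who are ADA positive but not fulfilling the conditions above for newly treatment-emergent ADA positive". This is a residual class.
- **OLE, newly persistently positive.** Negative at OLE baseline, then either positive at two or more assessments at least 16 weeks apart or positive at the last one. There is no condition on DB history.
- **Adverse events.** DB and OLE events are tabulated by "ADA status (i.e. ADA negative, (newly) TE-ADA positive, and non-TE-ADA positive) over safety analysis set and OLE analysis set" respectively.
- **On-study period.** ADA responses are also derived from the baseline before the first DB dose, with eosinophil and PK summaries. No on-study table of adverse events by ADA status is specified.

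**The concern.** The two OLE routes to treatment-emergent status do not cover everyone who is negative at OLE baseline and then turns positive. A single positive DB sample closes the first route. The second needs a baseline titre, and SAP 8.7 reports titres for positive samples only; it sets a value for positives below 15 but none for negatives.

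The same rule is applied to both former arms, although DB was free of benralizumab for one of them. In a former placebo patient, a DB positive cannot be a response to the drug. Even so, it excludes that patient from ADA incidence on first exposure if the OLE baseline is negative.

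Immunogenicity is the secondary objective of the OLE, and the SAP intends to look at ADA in relation to hypersensitivity. The class labels therefore need to mean the same thing from one table to the next.

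**Working it through.** The plan states no ADA rate or count, so there is no figure to reproduce. The check is logical, followed by an illustration of scale.

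**1. Apply the rules to specific histories.** Samples are DB Weeks 0, 16, 24, 40 and 56 and OLE Weeks 80 and 112, as read from the protocol's schedules of activities (the OLE table is partly broken in the text). TE is treatment-emergent.

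| History (titres) | OLE rule | DB rule at OLE baseline | On-study rule | Newly persistently positive |
|---|---|---|---|---|
| Placebo, negative throughout DB; OLE 15, 15 | TE | TE | TE | yes |
| Placebo, 15 at Week 16 only; OLE 15, 60 | non-TE | TE | TE | yes |
| Placebo, 15 at Week 0 only; OLE 15, 60 | non-TE | TE | TE | yes |
| Benralizumab, 15 from Week 16 to 56; OLE 15, 15 | non-TE | non-TE | TE | no |
| Benralizumab, 15 at Weeks 16 and 24, then negative; OLE 15, 15 | non-TE | TE | TE | yes |
| Either arm, 15 at Week 56; OLE 60, 60 | TE | TE | TE | no |

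Rows 2, 3 and 5 show the conflict: the same patient is newly persistently positive and non-treatment-emergent.

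**2. Find every history on which the two rules differ.** Allow each of the seven samples to be negative, 15 or 60 (a 4-fold step), which gives 3^7 = 2187 patterns. The OLE rule and the DB rule at the OLE baseline disagree only where DB has a positive, Week 56 is negative and the OLE has a positive:

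- DB: 3^4 − 1 = 80 patterns with Week 56 negative and some earlier positive.
- OLE: 3^2 − 1 = 8 patterns with at least one positive.
- Disagreements: 80 × 8 = 640, all non-TE under the OLE rule and TE under the DB rule.
- Of these, the Week 112 sample is positive in 80 × (3 × 2) = 480, so the patient is also newly persistently positive.

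No pattern that is negative throughout DB changes class. These are counts of logical patterns, not patient frequencies. The Week 0 sample is counted as DB here; excluding it would remove only the 2 × 8 = 16 patterns whose sole DB positive is at Week 0.

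**3. Scale in the former placebo arm.** About 250 randomised 1:1 gives 125 per arm. Assume OLE entry *e* = 80–100%, positive at some time in DB *p* = 2–10%, and seroconversion on first benralizumab *q* = 5–15%, independent of DB history.

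- Correctly TE = 125·e·(1 − p)·q: from 100 × 0.90 × 0.05 = 4.5 to 125 × 0.98 × 0.15 = 18.4.
- Moved to non-TE, at most = 125·e·p·q: from 100 × 0.02 × 0.05 = 0.1 to 125 × 0.10 × 0.15 = 1.9.

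The second line is an upper bound because it takes every DB-positive placebo patient as negative at Week 56. Under these assumptions the share of responders missed is at most *p*.

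**4. Scale in the benralizumab arm.** If 5–15% are induced during DB, 100 × 0.05 = 5 to 125 × 0.15 = 19 such patients could enter the OLE. Those who are ADA positive in the OLE and not boosted are in the non-TE column of the adverse-event table.

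**The case against.** The strongest reply is that the class is called *newly* emergent and is measured from the OLE baseline. A benralizumab patient already positive at Week 56 with a flat titre has no new response in the OLE. That patient has been counted in DB incidence and is treatment-emergent in the on-study derivation. The DB rule applied at the OLE baseline gives non-TE as well (row 4). This stands: a reader might infer that such patients are missing from OLE incidence, but leaving them out is coherent.

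A reader might also infer that placebo patients who turn positive on their first benralizumab are misfiled in general. The documents do not support that. Those negative throughout DB, who are likely to be most of them, meet the first condition and count as incidence (row 1). The SAP itself expects few ADA-positive placebo patients.

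There are safeguards too. ADA analyses are by treatment group, all ADA results are listed, cumulative and first-time-positive summaries are planned, and the OLE is descriptive only.

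None of this closes the gap for the history in rows 2, 3 and 5. The on-study derivation does not repair it for placebo patients either: its baseline precedes the placebo period, so a positive on placebo already makes the patient treatment-emergent, and the response to first benralizumab is not isolated. Nor is there an on-study version of the adverse-event table.

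**Conclusion.** The defect is real but narrow. A patient with a DB positive, a negative OLE baseline and an OLE positive is put in the non-treatment-emergent class at any OLE titre, against the DB rule and against the SAP's own newly persistent category. For former placebo patients this undercounts ADA incidence on first exposure, by at most about 0.1 to 1.9 patients under the assumed rates.

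The second part concerns labelling, not incidence. In the OLE adverse-event table, antibodies induced by benralizumab during DB share the non-TE column with antibodies that pre-date any benralizumab. A reader might conclude that most of that column is mislabelled, or that the whole table and the OLE incidence are wrong. Neither follows: the documents give no ADA rates from which to estimate such a share, and the SAP defines non-TE only as a remainder, not as pre-existing positivity.

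**What to change.** Amend the OLE part of SAP 8.7:

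1. **Randomised to placebo.** Define treatment-induced as ADA negative at OLE baseline and positive at least once afterwards, and boosted as a 4-fold or greater rise over a positive OLE baseline titre, regardless of DB samples.
2. **Randomised to benralizumab, with a DB positive, a negative OLE baseline and an OLE positive.** Assign an explicit class consistent with newly persistently positive. Note that patients already treatment-emergent in DB are also counted in DB incidence.
3. **OLE adverse events by ADA status.** Show patients who were treatment-emergent in DB, are still positive and are not boosted in a category of their own. Keep non-TE for all other ADA-positive patients, including placebo patients first positive during DB and still positive at OLE baseline without a 4-fold rise, so that nobody is left without a class.

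The cost is a change of SAP wording, re-derivation of one variable from data already collected, and one extra row or column in the table, before the final database lock. OLE adverse-event tables by ADA status are not among the summaries SAP 4.2.10.1 names for the primary lock.

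### SAP 8.7: one positive at the last sample counts as 6- and 12-month ADA persistence, and some baseline-positive OLE patients, including always-positive early stoppers, are labelled transient

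*SAP*

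**What the plan says.** SAP section 8.7 derives ADA categories for the double-blind (DB) period, the open-label extension (OLE) and the whole on-study period.

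*On-study.* Two duration-named categories apply to patients who are ADA negative before the first DB dose. The 12-month category takes two or more post-baseline positives "with ≥ 12 months between first and last positive) or positive at the last available post baseline assessment". The 6-month category is built the same way. The on-study list for the eosinophil summaries names a plain persistently positive row alongside these two.

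*OLE.* The baseline is reset: "Baseline value for the OLE period is based on the last available value collected prior to the 1st dose in OLE", nominally Week 56. Three categories follow:

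- The newly persistent class takes patients negative at OLE baseline, with two or more positives "with ≥ 16 weeks between first and last positive) or positive at last post-baseline assessment"; either route is enough on its own.
- The stable persistent class has a single route, given as "Patients who are ADA positive at baseline and ≥ 2 post-baseline assessments (with ≥ 16 weeks between first and last positive". There is no last-assessment alternative.
- The transient class is the remainder, described as "having at least 1 post-baseline ADA-positive assessment and not fulfilling the conditions of either newly persistently positive or stable persistently positive". There is no condition on baseline.

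*DB, for comparison.* The transient class does carry a baseline condition: "Patients who are transiently ADA positive, defined as ADA negative at baseline and at least one post-baseline ADA positive measurement".

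*Sampling.* Protocol Table 2 schedules ADA at Weeks 0, 16, 24, 40 and 56. I read Table 3 as scheduling it at Week 80 and at Week 112 (follow-up or IP discontinuation visit). Protocol section 7.1.1 gives a patient who stops IP in the OLE one visit, 8 weeks after the last dose, and nothing further.

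**The concern.** A category named for 6 or 12 months states a duration. The last-sample alternative requires none, so the label and the rule disagree.

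In the OLE the two persistent classes are built differently. The baseline-negative class accepts a positive last sample; the baseline-positive class does not. Transient is the residual class and, unlike in the DB period, admits baseline-positive patients. A patient with more evidence of continuing ADA can therefore receive the weaker label.

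Immunogenicity is a stated secondary objective for both periods (SAP Tables 1 and 2). These categories are reported as counts, percentages and maximum titres, and they group the eosinophil and PK summaries. Followed literally, the 12-month row mixes long-lasting ADA with single late positives, and the OLE transient row mixes resolved ADA with ADA that was never seen to resolve.

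**Working it through.** The plan gives no figure to reproduce. The check applies the rules literally to every positive/negative pattern at the scheduled weeks.

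**Inputs.** On-study post-baseline samples: Weeks 16, 24, 40, 56, 80, 112. DB-only samples: Weeks 16, 24, 40, 56. OLE samples: Weeks 80 and 112. I take 6 and 12 months as 26 and 52 weeks. This choice is not sensitive at nominal visits: the gaps between samples on either side of 12 months are 40 and 56 weeks, and on either side of 6 months 24 and 32 weeks.

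**1. On-study, full schedule, baseline negative.** Patterns with at least one positive: 2^6 − 1 = 63.

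- Positive at Week 112: 2^5 = 32 patterns, all labelled 12-month.
- Negative at Week 112 but with a span of at least 52 weeks: Week 80 positive and Week 16 or 24 positive, 3 × 4 = 12 patterns.
- Total labelled: 32 + 12 = 44.
- Labelled with a true span of at least 52 weeks: 42. The other two are Week 112 alone (span 0) and Weeks 80 and 112 only (112 − 80 = 32 weeks).
- For the 6-month label the counts are 52 labelled and 51 with the duration. The exception is Week 112 alone.

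**2. On-study, DB samples only.** Maximum span: 56 − 16 = 40 weeks, below 52. Patterns with a positive: 2^4 − 1 = 15. Positive at Week 56: 2^3 = 8. All 8 get the 12-month label and none can show 12 months. The same 8 get the 6-month label, because without Week 56 the longest span is 40 − 16 = 24 weeks. For these patients the two categories are identical. Six of the 8 have a span of at least 26 weeks (Week 56 positive with Week 16 or 24 positive, 3 × 2).

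**3. OLE, allowing one sample to be missing.**

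| Week 80, Week 112 | OLE baseline positive | OLE baseline negative |
|---|---|---|
| +, + | stable persistent | newly persistent |
| +, missing | transient | newly persistent |
| missing, + | transient | newly persistent |
| −, + | transient | newly persistent |
| +, − | transient | transient |

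In rows two and three every available test of the baseline-positive patient is positive. Row four is not continuous positivity. In row five transient is a fair description for the baseline-negative patient; the DB rule would not apply it to a baseline-positive one.

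**4. OLE, always positive, IP stopped early, last sample 8 weeks after the last dose.**

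| Last dose (week) | OLE samples (weeks) | Span (weeks) | Label |
|---|---|---|---|
| 56, 60, 64 or 72 | one: 64, 68, 72 or 80 | – | transient |
| 80 | 80, 88 | 8 | transient |
| 88 | 80, 96 | 16 | stable, decided by visit timing |
| 96 | 80, 104 | 24 | stable |
| 104 | 80, 112 | 32 | stable |

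A baseline-negative patient with the same positive samples is newly persistent in every row.

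**The case against.** Four counter-arguments deserve weight.

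*The last-sample rule is a deliberate convention.* It also appears in the DB persistent and OLE newly persistent definitions, on the reasoning that resolution was not observed. That stands, and I do not dispute the convention. It does not rescue the duration-named rows, because the plain persistently positive row already carries it. A footnote would disclose the mixture but leave it in the count.

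*Patterns are not patients.* This stands. Removing the alternative changes 2 of 63 full-schedule patterns; the larger change, 8 to 0 of 15, is confined to patients with DB samples only. The documents give no ADA rate from which to predict numbers.

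*The 40-week ceiling may not hold for everyone.* This also stands. SAP section 3.1.1 describes off-treatment follow-up under protocol versions 1.0 and 2.0. Its ADA schedule is not in the current documents, so those patients may have later samples.

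*The raw information is reported anyway.* SAP 8.7 also plans by-visit, cumulative and first-positive tables and a listing of all ADA results, from which duration can be recovered. That limits the harm but does not make the category counts right.

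A reader might infer that always-positive patients in general become transient in the OLE. The documents do not support that: a patient positive at baseline, Week 80 and Week 112 has two positives 32 weeks apart and is stable persistently positive. A reader might also infer that safety or efficacy conclusions are compromised. AE summaries by ADA status use negative, treatment-emergent and non-treatment-emergent groups. Efficacy by ADA uses DB categories only, without formal comparison.

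**Conclusion.** The definitions are wrong as written in two specific respects.

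(a) The on-study 6- and 12-month categories admit patients with no demonstrated duration. One first-ever positive at Week 112 meets both. Patients with DB samples only can meet the 12-month label on the current schedule only through the last-sample alternative.

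(b) OLE baseline-positive patients with a post-baseline positive, but without two at least 16 weeks apart, are called transient. This includes always-positive patients whose last dose is at Week 80 or earlier, or who have one usable OLE sample because a visit was missed or a post-dose sample was excluded. Baseline-negative patients whose last sample is positive are called persistent on the same post-baseline results.

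The conclusion rests on nominal visit weeks, on my reading of the Table 3 sampling columns, and on an ADA sample being taken at the IP discontinuation visit. It concerns category counts for a secondary objective and the descriptive titre, eosinophil and PK summaries built on them at the final database lock. No co-primary or key secondary analysis is touched. It should be corrected because it is cheap to correct and the labels would otherwise mislead.

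**What to change.** **On-study.** Delete the last-assessment alternative from the 6- and 12-month categories and keep it in the general persistently positive row. Show patients who qualified for a duration-named row only through a positive last sample as duration indeterminate. The 12-month patterns fall from 44 to 42 of 63 (full schedule) and from 8 to 0 of 15 (DB only); the 6-month patterns fall from 52 to 51 of 63 and from 8 to 6 of 15.

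**OLE.**

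- Restrict transiently positive to patients ADA negative at OLE baseline, as in the DB period.
- Count baseline-positive patients as stable persistently positive if they have two positives at least 16 weeks apart, or if all available post-baseline OLE samples are positive.
- Report the remaining baseline-positive patients with a post-baseline positive, such as (+, −, +) and (+, +, −) at baseline, Week 80 and Week 112, in a separate row.

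Simply adding the last-sample alternative to the stable class would not do: it would label (+, −, +) stable despite the negative at Week 80. Under the rule proposed here, every always-positive early stopper with at least one post-baseline sample becomes stable.

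**Cost.** SAP wording and re-derivation of flags from data already collected, before the final database lock. The 12-month and transient categories become smaller and two rows are added. No new sampling is needed and no analysis at the primary lock changes.
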